3. STUDY HYPOTHESIS

3.1 Primary objective

To determine the efficacy of MedCu copper oxide impregnated wound dressing for the management of lower limb ulcers, measured through wound status (healed vs non-healed) at 12 weeks post-baseline

3.2 Secondary objective

To determine the efficacy and safety of MedCu copper oxide impregnated wound dressing for the management of lower limb ulcers at 4, 8 and 12 weeks post-baseline

- Wound status (healed vs non-healed at 4 and 8 weeks)
- Healing rate (ulcer size, PUSH score)
- Generic quality of Life (EQ-5D-5L)
- Lower limb symptoms (VEINES Sym)

4. STUDY PROTOCOL

4.1 Study design and timeline

This concerns a prospective randomized controlled trial. The study will be carried out by North Cumbria Integrated Care NHS trust. Up to two other NHS Trusts will be considered for inclusion in the trial as recruitment sites once the trial has been listed on the National Institute for Health Research national portfolio. The study will take place in local community and hospital settings with support and oversight from research staff. Research delivery staff will be delegated to provide support with data collection and processing.

Table 2. Anticipated timeline

| Month | Setup | Recruitment | Analysis | Finalise |
|--------|-----------------------------|---|--------------|-------------------------------|
| Jan-25 | Submission for HRA approval | | | |
| Feb-25 | NIHR portfolio adoption | | | |
| Mar-25 | HRA and Trust approval | Start recruitment; first patient, first visit | | |
| Apr-26 | | Finish recruitment | | |
| Jul-26 | | Last participant, last visit | | |
| Aug-26 | | | Analyze data | |
| Sep-26 | | | | Finalise analysis & report |

4.2 Participant identification & screening

Patients who are referred to the local clinical team with a lower limb ulcer will be screened for eligibility for this study by the direct care team. The research team will then be informed on potential participants and the patient information sheet will be added to the appointment letter. All eligible patients will be invited to take part until the required numbers have been achieved. Patients

will be recruited sequentially and be allocated into one of two randomisation groups. The eligible patient population is defined in the Inclusion and Exclusion criteria section.

There may be occasions where the consent may be delegated to a member of the research team; this is an option as long as the patients has given verbal consent for this when asked by the direct care team first. During the first appointment, the study will be discussed in further detail and the participant has the opportunity to ask questions that they may have. If potential participants meet the eligibility criteria, the patients can be consented by the direct care team personnel or this may be delegated to the research delivery team (again, as long as the patient's verbal consent has been sought for the latter arrangement). A screening form will be completed for potentially eligible patients to confirm that they indeed meet the trial criteria.

Participants will receive no incentives and consent will be regarded as a process and not a one off event. Participants are free to withdraw from the study at any time without the need to give any reasons for withdrawal. Their standard care will not be affected by either declining to participate in the study or withdrawing during participation – patients would still be managed with an approved type of wound dressing even if not in the trial.

4.3 Recruitment

Participants will be allocated to one of two randomisation arms. Patients in both arms will be given standard supportive advice on lower limb ulcers, to include compression bandaging, and their general management.

All participants will have demographic data obtained and the following measures (table 3):

Table 3. Baseline measures

| Weeks | 0 | 2 | 4 | 6# | 8 | 10 | 12# |
|--|---|---|---|----|---|----|-----|
| Baseline measures (demographics, medical history, vascular history) | Х | | | | | | |
| Ulcer wound status + dressing use status | Χ | | Х | | Х | | Х |
| Ulcer size, digitally measured with Healthy io App | Χ | | Х | | Х | | Х |
| PUSH score | Χ | | Χ | | Χ | | Χ |
| EQ-5D-5L | Χ | | | | | | Χ |
| VEINES Sym | Χ | | Χ | | Χ | | Х |
| Photo of ulcer (or original index site); subject to additional consent by patient (recorded with Healthy io App) | Х | | Х | | Х | | X |

Allowed to be up to 2 weeks early or late. For all follow-up dates, calculation is based on original enrolment date for patient, even if deviation for one or more follow-up timepoints.

The Pressure Ulcer Scale for Healing (PUSH) tool, see Appendix 1 is a standardised method of assessing and monitoring the severity and healing of both pressure ulcers and venous leg ulcers (Stotts et al, 2001; Ratliff & Rodeheaver 2005). Concerns have been raised regarding the criterion

validity and intra-rater reliability of the tool (Pillen et al 2009) however in the absence of other valid tools it provides a comprehensive parallel assessment of the ulcer along with measuring size alone.

VEINES-Symptoms is a patient reported outcome measure score that focuses on lower limb health, and can be used in patients both with, or without a lower limb ulcer (Launois 2015)

During the recruitment process the research team acts as a contact point and coordinator for patients requiring information and support. If concerns are raised on participants (mental) wellbeing based on the home visits or outcome of the assessments, referral of patients/families on to other professional agencies will be done as appropriate and according to the Trust guideline.

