| | Participants must not be palliative and have the mental and physical capacity to provide informed written consent and complete patient reported outcome measures. Participants are recruited from the local hospital / community clinics. |
|--------------------|---|
| Sample size | The primary outcome, wound status (healed vs non-healed) is used for sample size calculation. Treatment will be random and 1:1 allocation: n = 33 standard of care and n = 33 MedCu copper dressing cases, giving a combined total of n = 66 participants. |
| | The sample size calculation is based on 2x2 Chi-squared test (80% power and 5% alpha). The hypothesis is a minimum 20% (effect size 0.40) difference in wound healed at week 12, with then allocation for 30% withdrawal/dropout rate added. |
| | Option to expand sample size, subject to review of safety data, after initial sample size has been reached. This then allows wound healing comparison for purer sample of 'leg ulcers' and 'foot ulcers' separately from each other. For each of these subsamples, 66 participants are to be recruited. |
| Sponsor | North Cumbria Integrated Care NHS Foundation Trust |
| Funder | Creed Health [name] [contact] Email: [contact] E: [contact] W: https://www.creedhealth.co.uk/ |
| Chief Investigator | [name], vascular specialist nurse, Vascular Surgery Dept, North Cumbria University Hospitals NHS Trust, Cumberland Infirmary, [name] [contact] |
| Co-investigators | [name] PhD, Research Project Lead, [contact]; Cumbria Partnership NHS Foundation Trust R&D Department, Cumberland Infirmary, [name] [contact] |
| | [name], Head of Podiatry, North Cumbria Integrated Care NHS Foundation Trust, Cumberland Infirmary, [name], [contact] |

| Organisations where research will take place | North Cumbria Integrated Care NHS Foundation Trust Cumberland Infirmary, [name] | | | |
|--|--|--|--|--|
| | Optional: up to 2 other NHS Trusts, exact sites to be determined (once trial has been listed on National Institute for Health Research National Portfolio) – amendment to be | | | |
| | submitted to HRA once additional site identified. | | | |
| Planned timeline | First patient, first visit: 1Mar2025, | | | |
| | Last patient, first visit: 31Apr2026 | | | |
| | Last patient, last visit: 30Jul2026 | | | |
| | Trial end date: 30Sep2026 | | | |

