4.5 Outcome measures

4.5.1 Primary outcome measures

Wound status (healed vs non-healed)

In line with the definition used by the VenUS6 research trial team, the primary outcome of this trial is time to healing of the reference ulcer, and the definition is: complete epithelial cover in the absence of a scab (eschar) with no dressing required. There is no minimum length of time that the index site has to have been in said condition for when participant present for follow-up study visit.

4.5.2 **Secondary outcome measures**

Clinical outcome measures

- ulcer size, measured digitally with Healthy io App
- Size and characteristics of ulcer, determined with PUSH score
- Quality of life score, determined with EQ-5D-5L score.
- Patient discomfort related to legs, VEINES Sym questionnaire

- Patient withdrawal rates due to change in management (e.g. need for surgery)
- Lower limb ulcer infection rates
- Types of dressing used in the standard care arm (non-antimicrobial and antimicrobial)

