5. SUBJECTS

5.1 Anticipated number of research subjects

Below a summary is given for the sample size needed. The primary outcome, wound status (healed vs non-healed) is used for sample size calculation for both randomisation groups.

The sample size calculation has been performed using GPower freeware sample size calculator, based on 2x2 Chi-squared test for wound healed status. Power calculation for sample size assumes 80% power and 5% two-sided confidence interval.

Table 4: standard care vs MedCu dressing. The hypothesis is that MedCu dressing performs better to a minimum 20% (effect size 0.41) in wound healed at week 12.

Since some patients may withdraw over the course of the 12-week trial period, a 20% dropout rate is calculated into each sample size. A 1:1 allocation to the two types of dressing is applied.

Note: There will be an option to expand sample size, subject to no safety concerns after initial sample size has been reached. This then allows wound healing comparison for purer sample of 'leg ulcers' and 'foot ulcers' separately from each other. For this purpose, the same effect size will be applied. The hypothesis is that MedCu dressing performs better to a minimum 20% (effect size 0.40), requiring a sample size 66 (taking into account same 30% drop-out/withdrawal rate)

Table 4, Sample size calculations

| | Sample size calculation | | | | | |
|------------------|---|---|--|--|--|--|
| | Standard care control dressing | Intervention dressing (MedCu copper dressing) | | | | |
| Ulcer healed | 40% | 60% | | | | |
| Ulcer not healed | 60% 40% | | | | | |
| | Power beta of 80%, Alpha p-value of 0.05, effect size 0.40 Sample size required without any drop-out: 50 patients Sample size with 30% attrition rate included: 66 patients Total of 66 patients, distributed as: - 33 Patients to receive MedCu dressing - 33 Patients to receive standard care dressing | | | | | |

The CONSORT guidelines require a statement on the number of patients assessed for eligibility (Schulz, Altman & Moher 2010). The number of patients screened but who did not meet the inclusion criteria or who declined to participate will be recorded, as will any patients who are lost to follow-up (Appendix 5).

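### The week-12 wound status reading, the only primary assessment, may be taken from week 10 to week 14, with no rule tying an early or late reading to week 12

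*Protocol*

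**What the plan says.** The primary objective (Protocol, section 3.1) is efficacy "measured through wound status (healed vs non-healed) at 12 weeks post-baseline". Section 4.5.1 defines healing by the state of the index site at the follow-up visit and adds: "There is no minimum length of time that the index site has to have been in said condition". The same section also says that "the primary outcome of this trial is time to healing of the reference ulcer", which does not agree with a binary status at one time point.

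Table 3 (section 4.3) puts the mark # on weeks 6 and 12. The note beneath reads "Allowed to be up to 2 weeks early or late". The mark is not repeated before the note in the text at hand, but the table has no other mark that the note could explain. Visit dates do not drift: "For all follow-up dates, calculation is based on original enrolment date for patient, even if deviation for one or more follow-up timepoints". Week 6 has no assessment in the table. Weeks 4 and 8 have assessments but carry no mark. So the only data-bearing visit with this tolerance is the primary one.

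Section 5.1.1 says participants cannot be blinded and claims blinding only for the statistical analysis. Under section 4.4 the nurse who applies the allocated dressing also measures the ulcer. Section 7.2 compares the arms by a chi-squared test. Table 4 plans on 40% healed with standard care and 60% with MedCu.

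**The concern.** Healing accumulates over time, so a status read at week 10 and one read at week 14 do not measure the same thing. The protocol treats both as week 12 and gives no rule for relating either to day 84. An ulcer that is open on day 70 and closes on day 80 is recorded as not healed at 12 weeks, although it was. One that closes on day 95 can be recorded as healed at 12 weeks, although it was not.

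If visits fall later on average in one arm, that arm gains healed ulcers for a reason unrelated to the dressing, and the stated test cannot separate the two. The allocation is visible and the timing within the window is free, so such an imbalance could arise without any protocol deviation. A later analysis plan can adjust for visit time, but it cannot recover day-84 status when the only reading was taken on day 70.

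**Working it through.** **Inputs.** Visit limits: 12 − 2 = 10 weeks (day 70) and 12 + 2 = 14 weeks (day 98), from the Table 3 note. Healed at week 12: 40% and 60%, from Table 4. Per-arm numbers: 25 (Table 4's 50 without dropout, halved) and 33 (its 66, halved). Table 4's 50 reproduces from a 1-df chi-squared test with its stated effect size of 0.40, 80% power and alpha 0.05, and 50 × 1.3 = 65, made even, gives 66. Whether 0.40 suits a 40% v 60% comparison is a separate question and does not enter here.

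**Assumption.** The protocol gives no distribution of healing times. I use F(t) = 1 − (1 − p)^((t/12)^k), where p is the week-12 proportion. k = 1 is a constant hazard; k = 0.5 and k = 2 show the range.

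**Step 1: change within one arm (k = 1).**
- Standard care, week 10: 1 − 0.6^(10/12) = 34.7%; week 14: 1 − 0.6^(14/12) = 44.9%. Span 10.2 points.
- MedCu, week 10: 1 − 0.4^(10/12) = 53.4%; week 14: 1 − 0.4^(14/12) = 65.7%. Span 12.3 points.
- With k = 0.5 the spans are 5.1 and 6.2 points; with k = 2 they are 20.2 and 24.2.

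**Step 2: same timing in both arms (k = 1).** The arm difference is 18.7 points if all are seen at week 10, 20.0 at week 12 and 20.8 at week 14. It moves by at most 1.3 points (2.8 with k = 2: 17.2 against 20.0).

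**Step 3: different timing, no true effect (40% in both arms at week 12).** The false difference is F(later) − F(earlier). Type I error is the two-sided rejection probability of the uncorrected chi-squared test, by exact enumeration of two binomials with k = 1.

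| Mean timing, weeks | False difference, k = 1 | Range, k = 0.5 to 2 | Type I error, 25 per arm | Type I error, 33 per arm |
|---|---|---|---|---|
| 12 v 12 | 0 | 0 | 6.0% | 5.9% |
| 11.5 v 12.5 | 2.6 points | 1.3 to 5.1 | 6.5% | 6.5% |
| 11 v 13 | 5.1 points | 2.6 to 10.2 | 7.8% | 8.2% |
| 10 v 14 | 10.2 points | 5.1 to 20.2 | 13.1% | 15.2% |

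The first row exceeds 5% because the test is discrete at these sizes, so increases should be read against about 6%.

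**Step 4: true 20-point effect, full split (k = 1).** MedCu seen at week 10 and standard care at week 14: 53.4 − 44.9 = 8.5 points. The reverse: 65.7 − 34.7 = 31.0 points.

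**The case against.** The strongest reply is that timing need not differ between arms. Dates are anchored to enrolment, section 4.4 places the researcher's visit at week 12, and nothing in the protocol says that visits may be chosen by how the wound looks or who schedules them. With shared timing the comparison is almost unaffected. This stands, and it limits the size of the point. A reader might set the 10 to 12 points beside the 20-point target and infer that the window alone could supply half the effect. That compares a change within one arm with a difference between arms. A false 10-point difference needs one arm seen entirely at week 10 and the other entirely at week 14, and nothing in the protocol suggests that.

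A reader might also infer deliberate steering of visits. The protocol permits it but gives no evidence for it, and seeing a truly stalled ulcer early would change nothing, since it is open at either date. Unblinded assessment and the lack of a minimum healed duration are separate weaknesses that a narrower window does not cure.

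A third tempting inference is that the window breaks the timeline: 30 April 2026 plus 14 weeks is 6 August, after "Last patient, last visit: 30Jul2026". This is minor. The dates are planned ones (the summary's recruitment end, 31 April, does not exist), 30 April plus 12 weeks is 23 July, and section 9.4 ends the study at the actual final visit.

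What the reply does not remove is the misclassification of individual patients, or the absence of any rule for it.

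**Conclusion.** The point holds as a weakness in how the primary outcome is fixed, and it should be corrected; it does not invalidate the design. The week 10 to 14 window, the 12-week endpoint and a test that ignores visit time are all in the protocol. The sizes are not: they rest on an assumed healing curve, and the documents cannot narrow the range in the working. Under a constant hazard, imbalances of 1 to 2 weeks produce about 3 to 5 false points and add roughly 0.5 to 2 percentage points to the type I error. The figures of 10 points and 13–15% describe only the extreme split.

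**What to change.** For wound status only:
- Do not accept a visit before day 84 as the final reading of an unhealed ulcer, and narrow the late side, for example to day 91.
- Record the date on which the index ulcer was first seen healed and the actual date of the visit, and class status as of day 84 from these. State how a late first healed reading, and a recurrence before day 84, are counted.
- Add a sensitivity analysis that uses actual assessment time.

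Keep the wider window for the questionnaires, and remove the mark from week 6. Do not use dressing-change records as the fallback: an ulcer counts as healed only once it needs no dressing, so the records may be missing for the very patients who healed. Settle at the same time whether the primary outcome is status at week 12 or time to healing; the recorded dates serve either.

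The cost is an amendment to the wording, two date fields, somewhat tighter scheduling of one visit, and a few readings that will fall outside the window. Sample size and treatment do not change.

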4.4 Follow-up and Standard care

Patients are in the study for the planned 12 weeks, even if the index lower limb ulcer has healed prior to that time point. Apart from the specific research measurements and assessments, the patient will be followed up as they would in normal clinical practice. The vascular or community nurse will redress the lower limb ulcer as per allocated dressing choice, and will conduct the measurement of the lower limb ulcer (Healthy io App and PUSH score). The researcher will visit the patient at baseline (week 0), week 4, week 8 and week 12 of study participation to randomise the patient and conduct the questionnaires.

Patients identified in the community (primary care, podiatry, or non-vascular surgery dept) can be invited to participate in the study via the vascular surgery department.

Standard wound care will be provided throughout the trial period, as well as meeting any other medical needs that arise. The SIGN guidelines for leg ulcer care form the framework for management of the leg ulcers (https://www.sign.ac.uk/media/1058/sign120.pdf), and the NICE guildelines form the framework for the most common foot ulcer type, diabetic foot ulcers (https://www.nice.org.uk/guidance/ng19))

4.5 Outcome measures

4.5.1 Primary outcome measures

Wound status (healed vs non-healed)

In line with the definition used by the VenUS6 research trial team, the primary outcome of this trial is time to healing of the reference ulcer, and the definition is: complete epithelial cover in the absence of a scab (eschar) with no dressing required. There is no minimum length of time that the index site has to have been in said condition for when participant present for follow-up study visit.

4.5.2 **Secondary outcome measures**

Clinical outcome measures

- ulcer size, measured digitally with Healthy io App
- Size and characteristics of ulcer, determined with PUSH score
- Quality of life score, determined with EQ-5D-5L score.
- Patient discomfort related to legs, VEINES Sym questionnaire

- Patient withdrawal rates due to change in management (e.g. need for surgery)
- Lower limb ulcer infection rates
- Types of dressing used in the standard care arm (non-antimicrobial and antimicrobial)

5. SUBJECTS

5.1 Anticipated number of research subjects

Below a summary is given for the sample size needed. The primary outcome, wound status (healed vs non-healed) is used for sample size calculation for both randomisation groups.

The sample size calculation has been performed using GPower freeware sample size calculator, based on 2x2 Chi-squared test for wound healed status. Power calculation for sample size assumes 80% power and 5% two-sided confidence interval.

Table 4: standard care vs MedCu dressing. The hypothesis is that MedCu dressing performs better to a minimum 20% (effect size 0.41) in wound healed at week 12.

Since some patients may withdraw over the course of the 12-week trial period, a 20% dropout rate is calculated into each sample size. A 1:1 allocation to the two types of dressing is applied.

Note: There will be an option to expand sample size, subject to no safety concerns after initial sample size has been reached. This then allows wound healing comparison for purer sample of 'leg ulcers' and 'foot ulcers' separately from each other. For this purpose, the same effect size will be applied. The hypothesis is that MedCu dressing performs better to a minimum 20% (effect size 0.40), requiring a sample size 66 (taking into account same 30% drop-out/withdrawal rate)

Table 4, Sample size calculations

| | Sample size calculation | | | | | |
|------------------|---|---|--|--|--|--|
| | Standard care control dressing | Intervention dressing (MedCu copper dressing) | | | | |
| Ulcer healed | 40% | 60% | | | | |
| Ulcer not healed | 60% 40% | | | | | |
| | Power beta of 80%, Alpha p-value of 0.05, effect size 0.40 Sample size required without any drop-out: 50 patients Sample size with 30% attrition rate included: 66 patients Total of 66 patients, distributed as: - 33 Patients to receive MedCu dressing - 33 Patients to receive standard care dressing | | | | | |

The CONSORT guidelines require a statement on the number of patients assessed for eligibility (Schulz, Altman & Moher 2010). The number of patients screened but who did not meet the inclusion criteria or who declined to participate will be recorded, as will any patients who are lost to follow-up (Appendix 5).

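### Section 5.1 states both a 20% and a 30% dropout allowance, and at 30% the planned 66 patients leave about 46 evaluable, not the 50 that Table 4 requires

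*Protocol*

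**What the plan says.** Protocol section 5.1 describes a sample size calculation "based on 2x2 Chi-squared test for wound healed status", with 80% power and a two-sided 5% level. The paragraph below the statement of the hypothesis says that "a 20% dropout rate is calculated into each sample size".

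Table 4, in the same section, gives 50 patients before dropout and then "Sample size with 30% attrition rate included: 66 patients", split 33 and 33. Its stated inputs are "Power beta of 80%, Alpha p-value of 0.05, effect size 0.40", with healed proportions of 40% on standard care and 60% on the copper dressing. The text above the table gives a slightly different effect size: "MedCu dressing performs better to a minimum 20% (effect size 0.41) in wound healed at week 12".

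The note on optional expansion also uses 30%, calls it the same rate, and reuses 66 for each of the leg-ulcer and foot-ulcer subsamples. The Sample size row of the protocol summary agrees with Table 4: "with then allocation for 30% withdrawal/dropout rate added".

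So 30% appears in three places and 20% in one, and all of it is current text.

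**The concern.** There are two linked problems. First, a reader cannot tell which attrition rate the trial was sized for. Second, at the rate stated most often, the enrolled total does not deliver the evaluable number on which the power claim rests.

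Attrition matters directly here because section 7.2 restricts the primary chi-squared comparison to participants with available data. Each patient lost before week 12 drops out of the test, so a shortfall in evaluable patients becomes a loss of power. The same total of 66 would carry the shortfall into each expansion subsample, if the expansion is used.

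**Working it through.** **Inputs (all Protocol section 5.1).** Two-sided alpha 0.05; power 80%; 1:1 allocation; effect size 0.40 in Table 4 and 0.41 in the text, both taken as Cohen's w; 50 patients before dropout; 66 after; attrition 20% (text) or 30% (Table 4, expansion note, summary).

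**Step 1: reproduce the 50.** For a chi-squared test on 1 degree of freedom, the noncentrality is N x w². With w = 0.40 and N = 50 this is 50 x 0.16 = 8.0, giving power of 80.7%. The smallest N reaching 80% is 50, so Table 4's base figure follows from its stated effect size.

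**Step 2: reproduce the 66.** Two ways of allowing for a dropout rate d were tried.

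| Rate d | 50/(1 - d) | 50 x (1 + d) |
|---|---|---|
| 30% | 71.4, so 72 | 65; by arm 25 x 1.3 = 32.5, so 33 per arm = 66 |
| 20% | 62.5, so 63 (64 for equal arms) | 60 |

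Only adding 30% and rounding up within each arm gives 66. The protocol shows no formula, so this is the best-fitting reconstruction and not a documented step.

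**Step 3: what 66 leaves.** This does not depend on how 66 was reached. Power is by noncentral chi-squared.

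| Attrition | Evaluable | Power, w = 0.40 | Power, w = 0.41 |
|---|---|---|---|
| 30% | 66 x 0.70 = 46.2, about 46 | 77.4% | 79.4% |
| 20% | 66 x 0.80 = 52.8, about 52 | about 82 to 83% | above 80% |

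The break-even attrition is 1 - 50/66 = 24.2%, which is neither of the stated rates.

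**Step 4: the other stated effect size.** With w = 0.41 the required N is 47. At 30% attrition, 47/0.70 = 67.1, so 68 for equal arms, still two above 66.

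**Step 5: what this check does not cover.** For 40% versus 60% with equal arms, the four cell proportions are 0.20, 0.30, 0.30 and 0.20, against 0.25 in each cell under no association. Then w² = 4 x 0.05²/0.25 = 0.04, so w = 0.20, not 0.40. At w = 0.20, power is 29% with 50 evaluable and 27% with 46. The usual two-proportion formula asks for 97 per arm, 194 in total, before dropout. The inflation step matters more on that base: 194/0.70 = 277.1, so 278, whereas 194 x 1.3 = 252.2, so 253, of whom only 253 x 0.70 = 177 would remain.

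**The case against.** The strongest reply is that 66 is sufficient at one of the two stated rates. If 20% is what was meant, about 52 patients remain, 64 would have been enough, and there is no shortfall: the error is confined to the 30% in Table 4, the expansion note and the summary. This stands. A reader might infer that the trial is bound to finish below its target at the attrition it plans for. The documents do not support that, because they do not settle which rate is planned.

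A second reply is that 66 does follow from 30%, since the summary speaks of the 30% as added, and adding 30% to 25 per arm gives 33. This also stands as an account of where 66 probably came from, so it would be wrong to say that neither rate leads to 66. It does not defend the figure. Losing 30% of those enrolled is a fraction of the larger number, and keeping 50 requires division by 0.70.

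A third reply is that the loss is small and depends on the effect size. At 0.41 the power with 46 patients is 79.4%, about half a point short of 80%. That is right: the inflation formula is independent of the effect size, but the size of the power loss is not.

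The suggestion that 20% is a slip does not remove the point. If so, 30% governs and 66 is too few.

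**Conclusion.** The point holds in two parts. The contradiction between 20% and 30% is plain on the page, and nothing else in the protocol resolves it. At 30%, 66 patients leave about 46 evaluable, four fewer than Table 4 requires. Power is then about 77% at w = 0.40 (79.4% at w = 0.41) against the stated 80%; enrolling for 50 would take 72, six more. At 20% the total is adequate and the fault is one of wording.

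The figures assume that the stated effect sizes are Cohen's w and that patients without week 12 data leave the primary test, as section 7.2 implies. The multiplication by 1.3 is an inference, and the shortfall at 30% does not rest on it.

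The practical weight is modest. A reader might also infer that raising the total to 72 would give an adequately powered trial. It would not: 50 reproduces only with an effect size that does not correspond to 40% versus 60% in a 2x2 table. That is a separate and larger problem, and correcting the attrition step leaves it untouched.

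**What to change.** State one attrition rate in the summary, the section 5.1 text, Table 4 and the expansion note, and inflate by 1/(1 - rate).

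The option that needs no extra recruitment is to keep 66 and disclose what it buys on the protocol's own terms: 50 evaluable only if attrition is 24% or less, and about 46 evaluable with about 77% power (at w = 0.40) if it is 30%. Otherwise, on the present base of 50, the consistent totals are 72 at 30% or 64 at 20%.

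Any of these statements should follow correction of the base number, so that 50 is not restated as an adequate target for 40% versus 60%. The same formula should then be applied to the recalculated base and to each expansion subsample. The cost of this point alone is wording in four places and one restated figure.

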7.2 Primary outcome statistics

The primary objective for this pilot study wound healed status at week 12.

For comparative performance (superiority) analysis, any statistically significant difference (p-value < 0.05) between the two treatment arms will be determined with Chi-squared test.

Analyses will be performed on a per protocol basis, with only those participants that data is available for included in the analysis. Data will first be collated in Microsoft Excel, followed by analyses performed using SPSS v20.

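### The stated 80% power for 40% vs 60% healed with 50 evaluable patients is wrong: the chi-squared effect size is 0.20, not 0.40, and the power is about 29%

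*Protocol*

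**What the plan says.** Section 5.1 says that the sample size was computed in GPower, "based on 2x2 Chi-squared test for wound healed status". It adds: "Power calculation for sample size assumes 80% power and 5% two-sided confidence interval". Allocation is 1:1. Table 4 sets healing at week 12 to 40% on standard care and 60% on MedCu, and gives the result as "Power beta of 80%, Alpha p-value of 0.05, effect size 0.40 Sample size required without any drop-out: 50 patients", raised to 66 for 30% attrition.

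The effect size is stated three times for this one hypothesis:

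- Summary, sample size row: "The hypothesis is a minimum 20% (effect size 0.40) difference in wound healed at week 12".
- Section 5.1, text above Table 4: "MedCu dressing performs better to a minimum 20% (effect size 0.41) in wound healed at week 12".
- Table 4: 0.40.

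The expansion note in section 5.1 reuses 0.40 for separate leg-ulcer and foot-ulcer samples, each "requiring a sample size 66 (taking into account same 30% drop-out/withdrawal rate").

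Section 7.2 makes the chi-squared test at p < 0.05, described as a superiority analysis, the primary analysis. It also calls the trial a pilot: "The primary objective for this pilot study wound healed status at week 12".

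**The concern.** An effect size means something only with its index. In a chi-squared power calculation the index is w. For two equal groups healing at 40% and 60%, w is 0.20. A value of 0.40 in that calculation doubles the effect. Required sample size varies with 1/w², so doubling the effect cuts the sample to about a quarter.

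At stake is the power claim for the primary endpoint. If the true benefit is the 20 points that the protocol hypothesises, the planned test would miss it roughly 6 to 7 times in 10, against the 2 in 10 that 80% power implies. The same figure would size two further subsamples.

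**Working it through.** **Inputs** (all from section 5.1 and Table 4): healed 40% vs 60%; 1:1 allocation; 2x2 chi-squared test (1 df); two-sided alpha 0.05; power 80%; effect size 0.40; 50 evaluable; 66 enrolled; 30% loss. The expansion note and the summary also use 30%. One sentence of section 5.1 uses 20%.

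**1. Reproduce the plan's figure.** Power = P(noncentral χ² with 1 df and noncentrality N·w² > 3.84). With w = 0.40:

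- N = 49: power 79.96%
- N = 50: power 80.7%

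The smallest N reaching 80% is 50, which matches Table 4 exactly.

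**2. Effect size for Table 4's own proportions.** With 1:1 allocation the cell probabilities are 0.20, 0.30, 0.30 and 0.20. Under no difference each is 0.25.

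w = √[Σ(P − E)²/E] = √[4 × 0.05²/0.25] = √0.04 = 0.20

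The same formula gives w = 0.40 for 30% vs 70%, a 40-point difference.

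**3. Where 0.40 and 0.41 could come from.**

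- Cohen's h = 2·arcsin√0.6 − 2·arcsin√0.4 = 0.403
- One-sample goodness-of-fit w, testing 60/40 against a fixed 40/60: √(0.2²/0.4 + 0.2²/0.6) = 0.408

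The first resembles 0.40 and the second resembles 0.41. Neither is the w of a two-group comparison. Used properly in its own two-sample formula, h does not give 50 either: 2 × [(1.96 + 0.84)/0.403]² is about 97 per arm.

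**4. Sample size for 80% power at 40% vs 60%.**

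- Noncentral chi-squared, w = 0.20: 197 in total (196 gives 79.96%, 197 gives 80.2%)
- Two-proportion formula, two-sided: 97 per arm, 194 in total
- Other variants (one-sided, or with continuity correction): 154 to 214 in total

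No variant comes near 50. With 30% loss, 197/0.70 = 281.4, so about 280 would be enrolled.

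**5. Power for 40% vs 60% at the planned size.**

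| Evaluable | Noncentral χ², w = 0.20 | Exact, uncorrected Pearson |
|---|---|---|
| 46 (66 × 0.70 = 46.2) | 27.4% | 28.7% |
| 50 | 29.3% | 33.6% |
| 66 (no loss) | 36.9% | 41.4% |

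With a continuity correction or Fisher's exact test, the exact power at 25 per arm falls to 23.7%.

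**6. Difference detectable with 80% power at 25 per arm, control rate 40%.**

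- Noncentral chi-squared: about 40% vs 79% (39 points)
- Exact Pearson: about 40% vs 77% (37 points)

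**7. A check that needs no effect-size index.** Suppose the trial observes exactly what it hypothesises, 10/25 vs 15/25 healed. Then χ² = 50 × 0.20² = 2.0 and p = 0.16. With no dropout, 13/33 vs 20/33 gives χ² = 2.97 and p = 0.085. A test with 80% power for a difference would be significant when that difference is observed.

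**8. Precision at 25 per arm.** The 95% CI half-width for the risk difference is 1.96 × √(0.24/25 + 0.24/25) = 0.27, or 27 points.

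**The case against.** *The index is not named.* This stands as a limit on the explanation. A reader might infer that the authors computed Cohen's h and typed it into the chi-squared routine. The protocol does not say so, and its 0.41 fits a goodness-of-fit w (0.408) better than h (0.403). Either route roughly doubles the two-group effect, so the power result is the same.

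*A larger effect may have been intended.* Using w = 0.40 would suit about 30% vs 70%. The summary and section 5.1 both say 20%, and Table 4 tabulates 40% vs 60%.

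*It is a pilot, so power matters less.* Section 7.2 uses the word once, in the section that specifies a superiority test at p < 0.05, and the summary and section 5.1 claim 80% power. The label does not make that claim correct. Equally, a reader might infer from it that estimation was the real aim and that the risk difference must become the primary result. One word does not support that; it is a design choice for the sponsor.

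*The size of the shortfall depends on method and dropout.* True. Power for the planned uncorrected test ranges from 27% to 41% over the evaluable numbers and methods above. At the 20% loss in one sentence of section 5.1, about 53 would remain (66 × 0.80 = 52.8), which lies inside that range. No version approaches 80%.

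Nothing elsewhere in the protocol repairs the figure. The primary test is neither one-sided nor covariate-adjusted, and there is no sample size re-estimation. The expansion option adds separate samples of 66, not a larger primary comparison.

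**Conclusion.** The stated power is wrong for the stated difference. For 40% vs 60% healed, a two-sided 5% chi-squared test has about 27% power with 46 evaluable patients, 29% with 50 and 37% with 66 (exact Pearson: 29%, 34%, 41%). The stated 50 is about a quarter of the roughly 197 that 80% power requires. Each expansion sample of 66 has the same shortfall under the same rates.

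This rests only on the protocol's own rates, allocation, alpha and test. It does not rest on knowing how 0.40 arose. Nor does it follow that the trial has to be enlarged: 66 patients may be kept if the protocol states truthfully what they can show.

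**What to change.** **Required.** In the summary, section 5.1 (both the 0.41 and the 0.40), Table 4 and the expansion note, replace the effect size with w = 0.20 and remove the 80% power claim.

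If 66 is kept, restate the power by one method throughout. An asymptotic power should not be paired with an exact detectable difference. For example:

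> For 40% vs 60% healed (w = 0.20, two-sided 5%, noncentral chi-squared), power is about 27% with 46 evaluable patients and 29% with 50. With 50 evaluable, 80% power is reached only for about 40% vs 79% (about 39 points). A test of 40% vs 60% with 80% power would need about 197 evaluable patients (about 280 enrolled at 30% loss).

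The exact Pearson equivalents of the first two sentences are 29%, 34% and 40% vs 77% (37 points). State the power of each expansion sample in the same way, and use one dropout rate so that the evaluable number is clear.

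**Optional.** Report the risk difference with its 95% CI (half-width about 27 points at 50 evaluable) beside the chi-squared test, and describe the trial consistently as a pilot.

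**Cost.** A wording change with no extra patients if 66 is kept; the stated power becomes much less favourable. If 80% power for a 20-point difference is wanted, enrolment rises from 66 to about 280.
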